Data interpretations from interviews one month after completing the MS Online course and 12 months after completing the MS Online course will be performed individually at each time-point. Comparisons between data interpretations at the different time intervals will also be performed.

Student participation:

This protocol may be used towards a student PhD project in the future but at present, no student has been assigned to work on this research project.

Table 1: Summary of RCT time frame

Assessment/Measure	No. Questions	Timeframe							
		Screening	Baseline	Complete Online course	One month after Online course	6 months after Online course	12 months after Online course	2.5 years after Online course	
Informed consent	1		X						
Age	1	X	X						
MS type diagnosed	2	X	X			X	X	X	
MS duration	2	X	X			X	X	X	
Do you follow a MS-specific lifestyle program?	2	X	X			X	X	X	
Do you follow a MS-specific diet	2	X	X			X	X	X	
Sex and gender	2		X						
Residential address and country	1		X					X	
Country of birth	1		X						
Height/weight	2		X			X	X	X	
Comorbidities	2		X			X	X	X	
Marital status	1		X			X	X	X	
Education	1		X						
Employment status	1		X			X	X	X	
Alcohol and smoking	4		X			X	X	X	
Medications	4		X			X	X	X	
Perceived Social Support	12		X			X	X	X	
Lifestyle factors									
Physical activity: IPAQ-SF	7		X			X	X	X	
Meditation: MAQ	3		X			X	X	X	
Sun exposure	4		X			X	X	X	
Diet quality: DHQ	21		X			X	X	X	
Omega-3 intake: dose, frequency	3		X			X	X	X	

Vitamin D intake: dose, frequency	3	X		X	X	X
Health outcomes						
HRQOL: MSQOL-54	54	X		X	X	X
Disability: PDDS	1	X		X	X	X
Anxiety and depression: HADS	14	X		X	X	X
Fatigue: FSS	9	X		X	X	X
Self-efficacy: UWSE-6	6	X		X	X	X
Qualitative interviewing	(7)		X		X	

If clinically significant improvement in HRQOL subset scores in Intervention group from baseline, we will consider an amendment to the RCT to provide participants in the standard-care access to the intervention course

X

If no clinically significant improvement in HRQOL subset scores in Intervention group from baseline, the RCT will not be amended

X

Total no. quantitative data questions (not including qualitative)	5	166		159	166	160
---	---	-----	--	-----	-----	-----

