(PHC) and Mental Health Composite (MHC) scores derived from the MSQOL-54 for participants in the intervention and standard-care arm will be calculated in the intervention and standard-care arms.

We will consider amending the RCT protocol to allow participants in the standard-care arm access to the MS Online intervention course before the end of the study (ie before the 2.5-year follow-up) in the event:

- a) clinically significant increases in either the PHC and MHC scores of MSQOL-54 (≥ 5) (Osoba et al., 1998; Taphoorn & Bottomley, 2005) from baseline are found in participants in the intervention arm at the 12-month follow-up who are *adhering to lifestyle recommendations* of the Online Lifestyle modifications course, but
- b) clinically significant improvements in either PHC or MHC are not found in participants in the standard-care arm at the 12-month follow-up.

If clinically significant improvements in either the PHC and MHC scores of MSQOL-54 are not found between baseline and 12 months in participants in the intervention arm *adhering to lifestyle recommendations* of the MS Online intervention course, the RCT will continue to as described to the 2.5 year follow-up.

If there are no amendments to the study, all participants will be notified of the study arm they were allocated to at the completion of the study. All participants in the standard-care arm will be provided with a link to access the MS Online intervention course.

- X. Qualitative interviewing consisting of semi-structured interviews by trained qualitative interviewers will be conducted on a randomly selected subset of participants (approximately 15 participants from intervention and standard-care arms, respectively) will be performed within 1 month of and 12 months after completing the MS Online course.
- XI. During enrolment in the trial, participants in both arms of the RCT will be advised to continue with normal medical treatment with their existing neurologists and healthcare providers and to continue with their usual medications, as recommended by their physicians.

Intervention group (MS Online intervention course):

Structure of delivery

In a seven-module, seven-session, self-administered program, participants in the intervention arm would be presented with an integrated lifestyle modification program including information and

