The complete patient-reported questionnaire with approximately 150 questions has been found to take approximately 60 minutes to complete. Participants will be able to login and complete this questionnaire over time. The participants will be requested to complete this questionnaire on four separate occasions (baseline, 6 months, 12 months and 2.5 years) and due to previous studies that we have performed within the Neuroepidemiology Unit utilising questionnaires of a similar length over 7.5 years ((Marck et al., 2018; Weiland et al., 2018), we do not believe the questionnaire will create an unacceptable burden on participants.

Quantitative data analysis:

We will measure adherence to lifestyle modification recommendations in people with MS enrolled in the MS Online intervention and the MS Online standard-care arm (control) using validated patient-reported questionnaires.

We will examine and compare clinical and health outcomes of depression, anxiety, fatigue, disability, self-efficacy and quality of life in people with MS in the short-term (6 months and 12 months) and medium-term (2.5 years) in people enrolled in the MS Online Intervention course arm and people enrolled in the MS Online standard-care course arm.

Statistical analyses will enable us to examine whether a causal relationship exists between lifestyle factors and clinical and health outcomes in people with MS. These analyses are anticipated to be completed within 6-12 months of collecting data for short-term and long-term analyses, respectively.

Qualitative data:

Qualitative data will comprise edited transcripts of recordings from semi-structured interviews from 15 randomly selected participants from the intervention arm and the standard-care arm carried out within one month of completing the MS Online course and 12 months after completing the MS Online course (the same people will be interviewed at both time points).

Interviews will be digitally recorded and transcribed by voice recognition software. Data will be stored in a re-identifiable format and encrypted files will be securely stored as described in Section 10.

Qualitative data collection feasibility:

The qualitative component of the MSOC – RCT is similar to the qualitative component of the MSOC – Feasibility study we performed. This interviewing technique was found to be both effective and participants reported positive feedback following interviews.

Qualitative data analysis:

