9. STATISTICAL METHODS

9.1 SAMPLE SIZE ESTIMATION & JUSTIFICATION

The two primary outcome measures for this study are changes in Physical Health Composite (PHC) and Mental Health Composite (MHC) derived from the MSQOL-54. PHC and MHC are derived by combining scores of relevant subscales (Vickrey et al., 1995). For the proposed MSOC – RCT, sample sizes were calculated in order to detect a 5-point difference in the PHC and MHC scores (a minimum clinically meaningful change in these HRQOL measures, between the intervention and standard-care arms).

To further account for loss-to-follow-up from the study period, based upon MSOC - Feasibility results, we anticipated a 42% loss-to-follow-up between randomisation and follow-up at 12 months. It is likely

this level of loss-to-follow-up is an overestimate of what will be observed in the proposed MSOC – RCT due to redevelopment of the intervention based upon feasibility data, but this overestimate will account for participants in the standard-care course that request access to the MS Online Intervention course after unblinding at 12 months after participants undertake the MS Online Standard-care course.

Taking these factors into account, we estimate 1054 participants, 527 in each arm (1:1 allocation) with data at baseline and follow-up would give 80% power to detect a 5-point change in HRQOL across both PHC and MHC outcomes. This estimation of power is based on the mean PHC and MHC scores and their SD, which is the SD between groups at baseline.

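### The 12-month rule for considering control access requires no between-arm difference, Table 1 words it differently, and section 9.1 relies on a loss allowance to cover switching that would dilute the 2.5-year contrast

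*Combined protocol and SAP*

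**What the plan says.** All references are to the combined protocol and SAP.

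- **Section 6.1, item IX, the action.** "We will consider amending the RCT protocol to allow participants in the standard-care arm access to the MS Online intervention course" before the 2.5-year follow-up.
- **Condition (a).** Increases of at least 5 points in the MSQOL-54 composites "from baseline are found in participants in the intervention arm at the 12-month follow-up who are" adhering to the lifestyle recommendations. No adherence cut-off is given.
- **Condition (b).** "clinically significant improvements in either PHC or MHC are not found in participants in the standard-care arm at the 12-month follow-up".
- **Continuation clause.** "If clinically significant improvements in either the PHC and MHC scores of MSQOL-54 are not found between baseline and 12 months in participants" of the intervention arm who adhere, the trial runs on unchanged. A further sentence covers disclosure of allocation: "If there are no amendments to the study, all participants will be notified of the study arm they were allocated to at the completion" (that is, when the trial ends).
- **Table 1.** "If clinically significant improvement in HRQOL subset scores in Intervention group from baseline, we will consider an amendment to the RCT". This has no adherence restriction, no condition on the standard-care arm and no 5-point figure.
- **Section 6.1, quantitative data analysis.** "We will examine and compare clinical and health outcomes of depression, anxiety, fatigue, disability, self-efficacy and quality of life in people with MS", between arms, at 6 months, 12 months and 2.5 years.
- **Section 9.1.** "sample sizes were calculated in order to detect a 5-point difference in the PHC and MHC scores" between the two arms. It sets 42% loss from randomisation to 12 months, calls that a likely overestimate, and says the overestimate covers standard-care participants who ask for the intervention course. Section 8.3 applies the same 42% to completion of the course and all follow-up.

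Item IX makes 12 months and 2.5 years the times at which the primary objective is assessed.

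**The concern.** A decision that could end the controlled comparison before 2.5 years should rest on evidence that the arms differ. The rule in item IX asks for something else: a change from baseline in a self-selected part of one arm, and a separate verdict on the whole of the other. Change from baseline mixes any course effect with regression to the mean, time trends and the effect of taking any course. Adherers may also differ from non-adherers in ways that randomisation does not balance.

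The wording adds uncertainty. It does not say whether group means or responder proportions are meant, and the phrase joining the two composites leaves open whether one or both must rise. Table 1 gives a different rule.

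What is at stake is the 2.5-year follow-up. If controls are given the course, the allowance in section 9.1 is supposed to protect the analysis. A loss allowance compensates for missing people. It does not directly compensate for people who stay, respond, and have received the other arm's intervention.

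**Working it through.** **1. The plan's sample size.** Inputs from section 9.1: 527 per arm, 5 points, 80% power, 42% loss. Section 9.2 adds a Bonferroni correction but no numeric alpha; I assume 0.05/2 = 0.025, two-sided. No SD is given, so the figure cannot be reproduced directly. Solving back with z-values 2.2414 + 0.8416 = 3.083:

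- If 527 is the enrolled number (synopsis, section 8.3): 527 × 0.58 = 305.7 with data, and SD = 5 × √(305.7/2) / 3.083 = 20.05. Going forward, SD 20 needs 305 per arm, and 305/0.58 = 526, close to 527.
- If 527 already have baseline and follow-up data (the wording in section 9.1): SD = 5 × √(527/2) / 3.083 = 26.3.

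The documents do not settle which is meant.

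**2. Can the rule be met with no between-arm difference?** Read as group means, let adherers gain 5.1, controls 4.9 and non-adherers x, with a proportion p adhering. Conditions (a) and (b) are both met. The whole-arm difference is 5.1p + (1 − p)x − 4.9. With x = 4.9 and p assumed at 0.3, 0.5 or 0.7, it is 0.06, 0.10 or 0.14, effectively nil.

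A simulation gave adherers and controls equal true mean gains of 4 to 5 points. It assumed 305 controls, adherers as 30% or 50% of 305, SD of change 12 or 18, and correlation 0.6 between composites. The rule was met in:

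- 6–14% of runs if both composites must rise in adherers and neither in controls;
- 21–32% if either must rise in adherers and neither in controls;
- 23–44% if either must rise in adherers and not both in controls.

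**3. Item IX against Table 1.** Take +11 in the intervention arm, adherers included, and +6 in controls. Condition (b) fails, so item IX does not prompt consideration. Table 1 does, because it looks only at the intervention group.

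**4. Switching and 2.5-year power.** If a fraction c of the effect is lost from the contrast, power = Φ(3.083(1 − c) − 2.2414). This holds for any n and SD that give 80% power.

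| Controls switching | Full effect gained, analysed as randomised | Switchers dropped |
|---|---|---|
| 0% | 80% | 80% |
| 10% | 70% | 78% |
| 20% | 59% | 75% |
| 30% | 47% | 71% |

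If 10% switch and gain half the effect, c = 0.05 and power is about 75%. The last column uses 3.083 × √[2/(1 + 1/(1 − s))] for the first term, where s is the fraction switching.

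**5. Can slack in the 42% cover it?** On the enrolled reading, 10% full-effect switching keeps 80% power only if total loss is at most 1 − 0.58/0.9² = 28.4%. If switchers are dropped, the limit is 1 − 0.58 × (1 + 1/0.9)/2 = 38.8%. On the with-data reading there is no slack.

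**The case against.** The strongest reply is that item IX commits the team only to consider an amendment. It is not a stopping boundary or an automatic crossover, the 12-month comparison stands whatever is decided, and Table 1 may be shorthand. The synopsis frames the primary objective around participants who adhere, so condition (a) is not arbitrary, and an SAP still to be developed could supply the cut-off. All of that stands. It limits the severity, but it does not supply a between-arm contrast: the synopsis compares adherers with participants following the standard-care recommendations, whereas condition (b) uses the whole standard-care arm.

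The power figures are also open to challenge. Full effect in every switcher is the severe end: analyses are expected 6 to 12 months after data collection, so access might come late. Section 9.1 treats switchers under a loss allowance, which may mean they would be counted as lost; the milder column then applies. The adherence and switching rates are assumed, and the +5.1/+4.9 example is deliberately close to the threshold.

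Four stronger readings are tempting but not supported:

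- That improvement in both adherers and controls has no assigned outcome. Condition (b) then fails, so no amendment is prompted and the trial continues.
- That the 42% simply ends at 12 months. Section 9.1 says so, but section 8.3 applies it to all follow-up; the two need reconciling.
- That 12-month unblinding in section 9.1 contradicts item IX. Item IX puts disclosure at study completion only if there is no amendment, and section 9.1 is speaking of controls who request access.
- That failing to trigger when the arms truly differ harms the trial. It leaves the 2.5-year comparison intact.

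**Conclusion.** The concern holds, at the level of something the sponsor should change. As written, the 12-month rule can prompt early control access with no difference between the randomised arms, and Table 1 would prompt it in a case that item IX excludes. The statement that presumed excess loss covers switching is not shown to be true.

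The loss of 2.5-year power depends on how switchers respond and are analysed. At 10% switching, power falls from 80% to between about 70% (full effect, analysed as randomised) and 78% (dropped); at 30%, to between about 47% and 71%. These figures assume two-sided alpha 0.025 and 80% power before switching. Whether lower loss would offset them depends on what 527 means, which the plan leaves open.

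**What to change.** **Section 6.1, item IX.** Base the 12-month consideration on the baseline-adjusted between-arm difference in PHC and in MHC among all randomised participants, each with a 97.5% interval, judged against the plan's own 5-point difference; for example, an estimate of at least 5 points favouring the intervention. State whether one or both composites must meet it. An interval that merely excludes zero is too weak a trigger: at 80% power the standard error is 5/3.083 = 1.622, so exclusion begins at 2.2414 × 1.622 = 3.6 points. Because the primary objective is framed around adherence, keep the adherer comparison as supportive, with a stated cut-off.

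**Table 1 and section 8.3.** Reconcile Table 1 with item IX, and the period covered by the 42% in section 8.3 with section 9.1.

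**Section 9.1.** Replace the statement that the overestimate covers switching with the 2.5-year power under stated switching rates, fractions of effect gained and handling of switchers. Say whether 527 is enrolled or with data.

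**Analysis.** State that participants are analysed in their allocated arm, and that any 2.5-year result after control access is reported as early versus delayed access.

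**Cost.** These are wording changes plus a short power table; the 12-month data and comparison are already planned. The stated 2.5-year power will look less favourable, and a result after access no longer has an unexposed control. The example criterion is met only about half the time per composite if the true effect is exactly 5 points.

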Primary Objectives:	
To determine whether participants adhering to lifestyle modification recommendations outlined in the MS Online intervention course have clinically significant increased health-related quality of life (HRQOL) in both domains of physical and mental health compared with participants following recommendations of the MS Online standard-care course. These outcomes will be examined in the short-term (6 and 12 months) and in the medium-term (2.5 years).
 
That is, we aim to determine whether participants in the Online intervention course following recommended lifestyle modifications have clinically significant and material increases in Physical Health Composite (PHC) and Mental Health Composite (MHC) scores, as derived from the validated tool designed to measure HRQOL in people with MS (MSQOL-54) compared with participants following recommendations of the Online standard-care course.

Secondary Objectives	
To determine whether participants following the lifestyle modification recommendations in the Online MS intervention course have improved depression, anxiety, fatigue, disability and self-efficacy in the short-term and medium-term compared with people following recommendations of the Online MS standard-care course.

Inclusion Criteria:	
Eligible participants must:
 
 1. Be able to read, write, and speak English; 2. Be 18 years old or over; 3. Have a confirmed diagnosis of relapsing-remitting MS by a neurologist preceding recruitment; 4. Be able to access the internet and be able to view sessions.
Exclusion Criteria:	
Exclusion criteria of participants include:
 
 1. Experiencing any serious co-morbid chronic illness or neurological illness/injury other than MS that would threaten regular participation or significantly affect the outcome measures in its own right, such as motor neurone disease or stroke, as determined by the study investigators; 2. Currently participating in another study or self-management program involving modification of lifestyle.
Number of Planned Participants:	
1054 participants, 527 in each arm at 1:1 allocation (intervention and standard-care arm)

Investigational product:	
Not applicable

Safety considerations:	
Participation in the study poses no physical risk to participants as the proposed RCT involves taking part in an Online MS

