	
educational course and completing self-reported questionnaires and possibly two semi-structured qualitative interviews.
 
Any potentially psychological risks from participating in the study have been addressed by contingency plans to provide links to Online help resources and the contact details of study team members to provide further information for participants.

Statistical Methods:	
Analysis of outcomes:
 
Characteristics of quality of life (QoL) will be measured by the MSQOL-54, including physical and mental health composite scores and multiple subdomains. Linear regression will be used to determine cross-sectional and prospective relationships with QoL. Characteristics of disability will be assessed using linear regression. Characteristics of dichotomous clinically significant fatigue and depression will be assessed by log-binomial regression. Characteristics of self-efficacy composite scores will be assessed by linear and log-binomial regression for continuous and dichotomised self-efficacy, respectively. All models will be assessed for potential clinical and demographic confounders and appropriate adjustments will be made in analyses.

Subgroups:	Not applicable
Consumer Involvement	
Consumers have been involved in the co-design of the MSOC RCT. A consumer advisory group comprising of 6-8 people with MS in a series of focus groups was involved in the co-design of the MS Online intervention and standard-care course. The devised course was then tested in a feasibility study (MSOC – Feasibility) involving a subgroup of people with MS (n = 31) and the quantitative and qualitative outcomes of the MSOC – Feasibility study were used to co-design the MS Online intervention and standard-care courses in the proposed RCT.

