The proposed study aims to prospectively determine whether an Online MS Lifestyle Modification Course (the intervention arm) can deliver an evidence-based educational intervention that results in behaviour change which is sustained and is translated into improved health outcomes for people

with MS, and whether these effects are superior to the Online standard-care course (the control arm).

In this RCT, we will be comparing two interventions/products that were developed by researchers at the Neuroepidemiology Unit (NEU) at the University of Melbourne:

1. the MS Online intervention course that delivers information on diet, exercise, Vitamin D and omega-3 supplementation and stress relief/meditation
2. the MS Online standard-care course that delivers standard MS-related information that can be obtained through publicly-available Websites.

In people with MS, we aim to compare health outcomes of people enrolled in the intervention (the MS Online intervention course) with the control arm (the MS Online standard-care course) by assessing:

- assess the uptake and maintenance of recommended lifestyle modifications in a cohort of people with MS after undertaking an MS online educational lifestyle course compared with people undertaking an online standard-care course.
- assess whether people with MS undertaking an MS online educational lifestyle intervention course results in improved clinical outcomes and health outcomes of depression, fatigue, disability, and quality of life over the short-term and medium-term compared with people undertaking an online standard-care course.

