Evidence behind a dietary influence on MS disease activity and QOL: evidence on saturated fat, and evidence regarding diet and its relationships with MS onset and progression. Introduction to dietary plan and benefits of different food groups.

Session 3: Sunlight and vitamin D

Detailed background information about how vitamin D is made from the action of sunlight is presented, along with evidence supporting a role of vitamin D in MS disease activity. Recommendations for optimal levels of supplementation and blood levels are presented.

Session 4: Physical activity/Exercise

The benefits of exercise are explained for people with MS (neurological, cognitive, physical), how and why. In addition, evidence regarding the benefits of exercise will be presented. How to implement an exercise plan with video examples provided.

Session 5: Stress and stress reduction

Introduction to mental health and relevance in MS. Participants are introduced to the science behind stress and its link to inflammation/MS. Mind-body connection, meditation and other stress reduction techniques to supplement the practical sessions on meditation they receive throughout the program. How to develop a mental health and wellbeing improvement strategy.

Session 6: Family primary prevention

Participants are introduced to the issue of primary prevention of MS in close family members who are at increased risk of developing the disease, and strategies for reducing this risk. This session will cover risks associated with smoking and excessive alcohol intake and MS progression.

Session 7: Review and consolidation

Program overview and recap, and an outline of next steps to take. Advise on follow-up questionnaires for longitudinal follow-up, and link to forums for further engagement (aimed at enhancing retention).

Standard-Care Group (MS Online standard-care course):

Structure and mode of delivery:

The standard-care course will be structured and delivered in the same way as the intervention course. That is, the total length of course is six weeks (7 sessions, 2 sessions per week with 2 weeks of catch-up).

Content:

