8. PARTICIPANT SAFETY AND WITHDRAWAL

8.1 RISK MANAGEMENT AND SAFETY

There will be no physical distress to participants in the proposed study as the study involves watching an educational course and completing questionnaires online. The exercise component of the MS Online Course in both arms of the study recommends a gentle exercise regimen, if participants decide to implement recommendations, that would not be expected to cause harm.

The research team in conjunction with participants involved in the qualitative interviewing component of the MSOC – Feasibility study found that the MS Online course, questionnaires and qualitative interviewing posed very low psychological distress to participants.

While we do not anticipate potential psychological distress, the following contingency plans will be implemented to address any psychological distress that may arise:

Quantitative research risk management

To address any psychological distress associated with completing online questionnaires at baseline and after 6 and 12 months and 2.5 years after completing the MS Online Course, links will be

provided at the end of questionnaires to country-specific help resources that the participant could access in the event that completing the questionnaires has raised issues for the participant. Participants will also be provided with the contact details of study team members and reminded that they can make contact with a team member if completing the questionnaires has raised any issues for them.

With regards to the HADS survey, while it is a validated tool for assessment of depression, it is not a diagnostic tool. However, we will also provide relevant country-specific resources and/or provide information/links to country-specific help/information at the end of the HADS. Notably, the HADS is the final questionnaire in the survey so this information will be provided directly after answering questions with the greatest potential to cause distress.

Qualitative research risk management

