9.3 STATISTICAL METHODS TO BE UNDERTAKEN

Quantitative data analysis:

Clinically significant fatigue will be defined as a mean FSS > 5 (Krupp et al., 1989). Anxiety and depression will be defined as higher HADS (Zigmond & Snaith, 1983). The UWSE will be assessed as a continuous term and dichotomised at the median as there is no established cut off point indicating sufficient self-efficacy.

Characteristics of quality of life (QoL) will be measured by the MSQOL-54, including physical and mental health composite scores and multiple subdomains. Linear regression will be used to determine cross-sectional and prospective relationships with QoL. Characteristics of disability will be assessed using linear regression. Characteristics of dichotomous clinically significant fatigue, depression and anxiety will be assessed by log-binomial regression. Characteristics of Self-efficacy composite scores will be assessed by linear and log-binomial regression for continuous and dichotomised self-efficacy, respectively. Characteristics of perceived social support scores will be

assessed by linear regression. All models will be assessed for potential confounders and appropriate adjustments will be made in analyses.

Qualitative data analysis:

Audio recordings will be transcribed for analysis and stored within Nvivo Software (www.qsrinternational.com) to enable data management. Data analysis will be conducted within a qualitative paradigm using reflexive thematic analysis (Braun 2014). Reflexive thematic analysis is considered the most appropriate analytic process due its lack of grounding in a particular philosophy (Braun 2006), and as a method suitable to exploring people's experiences, views and perceptions (Braun 2014) and its allowing expression of results in a way accessible to those in the wider community. Reflexive thematic analysis also emphasises the importance of the researcher being deeply involved in the research. Data will be analysed by the process of data familiarisation, coding, and theme development and refining. Data extracts (quotes) will illustrate themes.

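### The risk text covers only gentle exercise among the physical risks of acting on the advice, and no listed item or planned analysis compares relapses or acute health events by arm

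*Combined protocol and SAP*

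**What the plan says.** On risk, the synopsis (Safety considerations) argues: "Participation in the study poses no physical risk to participants as the proposed RCT involves taking part in an Online MS". The rest of that sentence names only the course, the questionnaires and the interviews. Section 8.1 gives the same reason. Its one comment on acting on the advice is that the exercise component "recommends a gentle exercise regimen, if participants decide to implement recommendations, that would not be expected to cause harm". The contingency plans in 8.1 all concern psychological distress. Outside the risk sections, 4.2 describes lifestyle modification in general as low risk.

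The intervention covers more than exercise. Session 2 in 6.1 lists "Introduction to dietary plan and benefits of different food groups". Session 3 adds "Recommendations for optimal levels of supplementation and blood levels are presented". Section 4.3 says that the course "delivers information on diet, exercise, Vitamin D and omega-3 supplementation and stress relief/meditation".

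On data, neither 5.3 nor Table 1 lists a relapse, an adverse event or any other acute health event. Section 9.3 plans regressions for quality of life, disability, fatigue, depression, anxiety, self-efficacy and social support, for example: "Characteristics of dichotomous clinically significant fatigue, depression and anxiety will be assessed by log-binomial regression". It has no safety table. The only mention of adverse events for participants, in 8.2, is about withdrawing from the study.

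**The concern.** In a behaviour-change trial the exposure is following the advice, not watching the videos. The risk text mostly assesses the watching. Where it does consider following the advice, it stops at exercise and leaves out supplements and diet.

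The gap in the data matters more than the wording. Only people with relapsing-remitting MS are eligible, and sections 4.2 and 4.3 cite fewer relapses as part of the rationale. A relapse item would therefore inform benefit as well as harm. If the question is not asked during follow-up, analysts cannot recover the answer later.

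Access to the intervention is expected to widen. The standard-care arm gets it at study end, or possibly earlier: 6.1 item IX says that an amendment will be considered if the 12-month PHC and MHC results meet set conditions. Section 4.2 then plans free release worldwide. As written, neither step would have a count of relapses or acute events by arm behind it.

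**Working it through.** **1. Does Table 1 contain such an item?** I added the question counts of the rows marked at each time point.

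- Background rows repeated at every follow-up: MS type 2, MS duration 2, lifestyle program 2, MS diet 2, height/weight 2, comorbidities 2, marital status 1, employment 1, alcohol and smoking 4, medications 4, social support 12. Sum 34.
- Lifestyle rows: 7 + 3 + 4 + 21 + 3 + 3 = 41.
- Health outcome rows: 54 + 1 + 14 + 9 + 6 = 84.
- 6 months: 34 + 41 + 84 = 159 (stated 159).
- Baseline: 159 + 7 (consent 1, age 1, sex and gender 2, address 1, country of birth 1, education 1) = 166 (stated 166).
- 2.5 years: 159 + 1 (address) = 160 (stated 160).
- 12 months: 159, but 166 is stated. The excess of 7 equals the number of interview questions shown in the table. That is a plausible explanation only, because the row is labelled "Total no. quantitative data questions (not including qualitative").

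The listed rows account for three of the four totals, and none concerns relapses or acute events.

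**2. How far does that go?** It shows that the table is consistent with itself, not that it lists every survey question. Section 5.3 collects cultural background at baseline, which has no row in Table 1. It also describes two meditation questions where Table 1 counts three. The survey is an attachment that was not available. An unlisted relapse item is therefore unlikely, but not ruled out.

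**3. What could show harm indirectly?** Table 1 repeats vitamin D and omega-3 dose, PDDS, comorbidities, medications, MS type, HADS, FSS and MSQOL-54 at each follow-up. These could show supplement use, lasting disability, a new chronic condition or mean worsening. A relapse that resolves between surveys 6 to 18 months apart need not appear in any of them.

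**4. How precise would a new question be?** The documents give no event rate, so I assume that 10% to 30% per arm report an event. Section 9.1 gives 527 per arm and 42% loss by 12 months: 527 × 0.58 = 306. The 95% half-width for the difference, with equal rates p in both arms, is 1.96 × √(2p(1 − p)/n).

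| n per arm | p = 0.10 | p = 0.30 |
|---|---|---|
| 306 (12 months) | 4.75 points | 7.26 points |
| 263 (50% loss, assumed) | 5.13 points | 7.83 points |
| 210 (60% loss, assumed) | 5.74 points | 8.77 points |

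The last two rows are for 2.5 years, for which no separate loss figure is given.

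**5. Which recall windows?** Follow-up is timed from course completion (6.1 item VIII). A 6-month window at the first survey would miss the six-week course (about 1.4 months), so that survey should ask about the time since the course started. A 6-month window at 12 months and a 12-month window at 2.5 years then leave months 12 to 18 uncovered, which is 6/30 = 20% of the post-course period. A 6-month window at the last survey would leave 12/30 = 40%.

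**6. Burden.** 2/159 = 1.3%. At the 60 minutes per 150 questions given in 6.1, two questions take 2 × 60/150 = 0.8 minutes.

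**The case against.** The strongest reply is that this is a low-risk educational trial with safeguards. Section 4.2 calls lifestyle change low risk. Participants keep their usual treatment and clinicians (6.1 item XI), and serious comorbidity is excluded (7.3). The standard-care course uses the same seven modules. Supplement doses are recorded in both arms, and disability, fatigue, depression and anxiety are compared by arm. Early access for the standard-care arm is only something that the investigators would consider. A general question about health problems, with several points of uncertainty, would not find a rare supplement harm.

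Much of this stands. It limits the likely risk, and it means that wider access would not come without any harm-relevant data. But one general remark in the background is not an assessment of the supplement and diet advice. Usual care and exclusions reduce risk without recording events, and the indirect measures can miss a relapse that resolves.

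A reader might infer that the matching Table 1 totals prove that no relapse question exists. They do not (step 2). A reader might also infer that the advice is harmful or that participants are in danger. The documents give no doses and no event data, so they do not support that.

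**Conclusion.** The point holds as a gap in the risk text and in the planned data. For the physical risk of acting on the advice, the risk sections consider only exercise, although the intervention also recommends vitamin D supplementation, introduces a dietary plan and covers omega-3. On the protocol as written, relapses and acute health events cannot be compared by arm.

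The conclusion rests on 5.3, Table 1 and 9.3 describing what will be collected and analysed; the survey attachment could change it. No harm is shown and none can be sized. The only figure is the illustrative precision at 12 months, about ±5 to 7 percentage points, which depends on the assumed 10% to 30% event rate and the stated 42% loss. The change is worth making because it is cheap and the data cannot be recovered afterwards. The gap does not undermine the primary analysis.

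**What to change.** 1. Extend the risk text in 8.1, and the matching synopsis entry, to cover acting on the supplement and diet advice. The clinical content is for the investigators.
2. Add two neutral questions, identical in both arms, to each remaining follow-up survey: any relapse, and any new health problem that needed medical care. Do not tie them to having changed lifestyle. The 6-month survey should ask about the time since starting the course, the 12-month survey about the last 6 months, and the 2.5-year survey about the last 12 months. State that months 12 to 18 after the course are not covered.
3. Add to 9.3 a descriptive table of these events by randomised arm, with 95% confidence intervals for the difference. Make 6 and 12 months the main comparison, because the standard-care arm may get access afterwards. Note that the table shows excess over standard advice, not over no advice.

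A table of participants who worsen by the protocol's own thresholds (5 points on PHC or MHC, 1.9 on FSS, one PDDS step) is optional. Many in each arm would cross these by chance, so only the between-arm difference would be interpretable.

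The cost is an ethics amendment and a survey about 1.3% longer (0.8 minutes), with no visits or staff. The limits are self-report without medical records, the recall gap, and too little precision for rare events.
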